- 7. We will calculate the difference in scores pre and post intervention for the selected assessments (see above) for both the active (FACES) intervention group and the control group. This will provide an early indicator that the intervention may make some difference and would be worth exploring in a larger, multicentre study as well as determining future sample sizes.

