9.4 Study assessments - Baseline

Post-operative assessments should be carried out within two weeks of surgery, and only after the patient has been registered these include:

- 1. Diagnostic Assessment of Non-verbal Accuracy-2, Adult Faces (DANVA2-AF)²⁰ a computerised test showing 24 photographs of 4 different facial expressions for 2.5 seconds each. Normative scores are available by age for this measure and an abnormal score is defined as ≥ 1 Standard deviation from the norm).
- 2. Part 1 of Emotion Recognition and Social Inference: The Awareness of Social Inference Test (TASIT) uses short one-minute video vignettes to assess emotion and social inferences. There are three subtests that comprise the TASIT: Emotional Evaluation Test (EET); the Social Inference-Minimal (SI-M); and Social Inference-Enriched (SI-E), but only the EET subtest will be used in this study. In the EET subtest, actors portray seven different emotions with dynamic facial movements, tone of voice, postures and gestures through short vignettes. These emotions include happy, sad, angry, disgust, fearful, surprised and neutral. We will use data from the EET subtest for our analyses As A and B tests exist, we will use both tests to avoid learning effect.
- 3. The Toronto Alexithymia Scale-20 (TAS-20) this is the most widely used selfreported questionnaire to measure alexithymia and is comprised of 3 factors: 1)

ability to identify emotions (e.g., I am often confused about what emotion I am feeling); 2) ability to describe emotions (e.g., It is difficult for me to find the right words for my feelings); and 3) externally-oriented thinking (e.g., I prefer to just let things happen rather than understand why they turned out that way).

- 4. Patient reported quality of life. (EORTC QCQ30 with the BN20)
- 5. Patient's families quality of life (Caregiver Quality of Life Index-Cancer (CQOLC)http://www.midss.org/content/caregiver-quality-life-index-cancer-cgolc-

Quality of life questionnaires will be completed before the clinic visit. If patients or their carers become distressed by the topics raised in the quality of life questionnaires, they will be supported by members of the clinical research team during their clinic visit.

Stage 1 will be used to define which of the assessments patients are able to complete. These assessments will be used for stage 2.

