9.5 Randomisation

STAGE 1: This is a non-randomised study. All patients will undergo the FACES Intervention

STAGE 2: Patients will be randomised 1:1; half receiving the FACES intervention (active intervention) and the other half receiving the General Cognition Intervention (control intervention)

'A web-based central randomisation system supplied by Sealed Envelope will allocate the intervention.

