11.2.2 Stage 2 -Feasibility Assessments

- 1. To explore if we are able to screen patients with suspected high grade glioma attending clinic for deficits in emotional recognition. A deficit in emotional recognition is defined as scoring 11 or less on the emotional recognition test from the OCS-Bridge battery. To proceed with a larger, efficacy study we would need to be able to screen a minimum of 75% of new patients.
- 2. Acceptability will be assessed by calculating the percentage of screened patients that provided informed consent. The intervention will be considered feasible if at least 50% of patients meeting the eligibility criteria provided informed consent. This will be explored in more detail with the parallel qualitative study.
- 3. To Assess the compliance of the intervention and control arms, the percentage of patients who have completed all sessions will be calculated. Compliance will be concluded if at least 80% of patients complete all sessions.
- 4. Assess the acceptibility of the following established, validated outcome measures:
 - a. Diagnostic Assessment of Non-verbal Accuracy-2, Adult Faces (DANVA2-AF);
 - b. Part 1, which includes emotion recognition, of Emotion Recognition and Social Inference: The Awareness of Social Inference Test (TASIT);

IRAS: 270758 SCARF-BT Protocol Version Number: 1.1 c. The Toronto Alexithymia Scale-20 (TAS-20).

For each of these measures we will measure completion rates pre- and post-intervention. Acceptability will be explored further with our parrallel qualitative study.

- 5. To Assess the effect size of the intervention we will be assess changes in assessment measures (below) between the active (FACES) intervention group and the control group. Differences in scores will be assessed for:
 - a. DANVA 2-AF
 - b. TASIT using the TASIT version B at retest.
 - c. TAS-20 alexithymia.
 - d. QLQ30 and BN20 quality of life measures will be assessed using published minimal clinically important differences²⁵.
- 6. The difference between the Intervention group and the control group in Outcome Measures will be calculated together with 95% confidence interval. This will provide an early indicator that the intervention may make some difference and would be worth exploring in a larger, multicentre study as well as determining future sample sizes.

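### Stage 2 effect estimated from pre-post changes without baseline adjustment: a valid analysis, but usually less precise than the data already collected allow

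*Protocol*

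**What the plan says.** Section 7.6.2, outcome measure 7, defines the quantity: "We will calculate the difference in scores pre and post intervention for the selected assessments", for each arm. Section 11.2.2, item 5, turns this into the effect estimate: "we will be assess changes in assessment measures (below) between the active (FACES) intervention group and the control group". The measures listed there are DANVA2-AF, TASIT, TAS-20 and the EORTC quality-of-life scores with BN20. Item 6 adds the interval: "The difference between the Intervention group and the control group in Outcome Measures will be calculated together with 95% confidence interval". It gives the purpose as an early sign that the intervention "would be worth exploring in a larger, multicentre study as well as determining future sample sizes". No model or covariate is named.

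The same patient measures are taken at baseline. Section 9.4 says "Post-operative assessments should be carried out within two weeks of surgery, and only after the patient has been registered", and the flow chart (section 4) and the schedule (section 9.10) both place baseline assessment before randomisation.

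For TASIT, section 9.4 says "As A and B tests exist, we will use both tests to avoid learning effect", and section 11.2.2, item 5b, specifies "TASIT using the TASIT version B at retest". The baseline form is therefore A by implication, although no sentence says so.

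**The concern.** A change score subtracts the whole baseline value, as if the slope of post on pre were exactly 1. When the true slope is smaller, the subtraction adds baseline noise to the outcome and over-corrects any chance difference between the arms at baseline. A model that estimates the slope avoids both. The baseline scores are already being collected, so the only price is one degree of freedom.

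At stake is the width of the interval that is meant to indicate whether a larger trial is worthwhile, and the variance carried into the sizing of that trial. Nothing else in Stage 2 hangs on it.

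**Working it through.** **Inputs.** 19 evaluable patients per arm (section 11.4); 1:1 allocation (section 9.5); 95% interval (section 11.2.2, item 6). The protocol gives neither the SD of any score nor the pre-post correlation ρ. Both are assumptions here: results are in SD units, with ρ from 0.3 to 0.95 and the ratio of post SD to baseline SD, k, from 0.8 to 1.5.

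**The plan's own figure.** Section 11.1.2 gives 19 per arm for a 50-point difference in a proportion, 5% significance and 80% power. The two rates are not stated; take 0.25 and 0.75.
- Uncorrected, two-sided: n = (1.960·√(2·0.5·0.5) + 0.842·√(0.25·0.75 + 0.75·0.25))² / 0.5² = (1.386 + 0.515)² / 0.25 = 14.5, so 15.
- With continuity correction: (14.46/4)·(1 + √(1 + 4/(14.46·0.5)))² = 18.2, so 19.

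The figure reproduces. It concerns completion, not scores, so the analysis of scores does not affect it.

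**Precision with equal SDs.** Half-widths of the 95% interval for the arm difference:
- Change score: t₃₆·√(2(1−ρ)·2/19), with t₃₆ = 2.028.
- Baseline-adjusted post score: t₃₅·√((1−ρ²)·(2/19)·(1 + 1/34)), with t₃₅ = 2.030. The factor 1 + 1/34, that is 1 + 1/(2n−4), is the average cost of estimating the slope.

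At ρ = 0.5 the change score gives 2.028·√(1·0.1053) = 0.658. The adjusted score gives 2.030·√(0.75·0.1053·1.0294) = 0.579.

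| ρ (assumed) | Change | Adjusted | Ratio |
|---|---|---|---|
| 0.3 | 0.779 | 0.637 | 0.82 |
| 0.5 | 0.658 | 0.579 | 0.88 |
| 0.7 | 0.510 | 0.477 | 0.94 |
| 0.9 | 0.294 | 0.291 | 0.99 |
| 0.95 | 0.208 | 0.209 | 1.00 |

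The two are equal at ρ = 0.94. In large samples the variance ratio is (1+ρ)/2, which is 0.75 at ρ = 0.5. On that basis 19 × 0.75 ≈ 14 adjusted patients per arm match 19 analysed by change.

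**Unequal SDs.** The ratio of half-widths is t₃₅·√(k²(1−ρ²)·(1 + 1/34)) / (t₃₆·√(k² + 1 − 2ρk)).

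| k | ρ 0.3 | ρ 0.5 | ρ 0.7 | ρ 0.9 |
|---|---|---|---|---|
| 0.8 | 0.72 | 0.77 | 0.81 | 0.79 |
| 1.25 | 0.90 | 0.96 | 1.01 | 0.99 |
| 1.5 | 0.95 | 1.00 | 1.015 | 0.90 |

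The largest loss in the table is 1.5%. The adjusted residual variance can never exceed the variance of the change score, so the ratio is bounded by (2.030/2.028)·√(1 + 1/34) = 1.016.

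**Simulation.** With equal SDs, no treatment effect, a 1 SD shift between forms and 8,000 trials per value of ρ, the mean width ratios were 0.82, 0.88, 0.94, 0.99 and 1.00 at the five values of ρ. Coverage was about 95% and bias about zero for both methods. At ρ = 0.7 the adjusted interval was the narrower one in 83% of trials.

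**Chance imbalance.** The baseline mean difference has SD √(2/19) = 0.32. An imbalance beyond 0.3 SD therefore arises in roughly a third of such trials. At ρ = 0.5 and equal SDs the change score over-corrects it by (1 − 0.5)·0.3 = 0.15 SD.

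**TASIT forms.** Suppose form B differs from form A by a constant c. Each arm's mean change then contains c, and the difference between arms is (Δ_FACES + c) − (Δ_control + c) = Δ_FACES − Δ_control. The shift cancels between arms but remains in each within-arm change promised by section 7.6.2, item 7.

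**Later sizing.** At ρ = 0.5 the change-score variance is 2(1−0.5) = 1 and the adjusted variance 0.75, in units of the score variance. A later trial sized on the former would be 1/0.75 = 1.33 times as large as one designed for adjustment.

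**The case against.** The strongest reply is that the protocol names no model and rules no covariate out. A regression of change on arm and baseline gives the same treatment estimate and interval as the regression of post score on arm and baseline, so the wording is compatible with adjustment, and covariates for an exploratory estimate are often left to the statistical analysis plan. This stands in part: the protocol does not forbid adjustment. But it sets out the comparison of changes in two places, and an analysis plan that followed the text as written would inherit the unadjusted version.

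It is also fair that the size of the gain rests wholly on assumed correlations and SDs. It shrinks to about 1% at ρ = 0.9, and it is an expectation that a single trial need not show.

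A reader might infer more than the documents support:
- *That the change-score comparison is biased or invalid.* Randomisation makes it unbiased, and its coverage is nominal.
- *That adjustment gains at any correlation below 1.* That is the large-sample result under equal SDs; at 19 per arm break-even is near 0.94.
- *That using two TASIT forms distorts the between-arm effect.* Both arms take the same retest form, so a constant difference cancels.
- *That carer quality of life (CQOLC) has a baseline value for every patient.* Section 7.6.2, item 6, asks only interested family members, and section 11.2.2, item 5, does not list it.

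**Conclusion.** The point holds as a nearly free improvement to a valid analysis. With 19 per arm and equal pre and post SDs, baseline adjustment narrows the expected 95% interval by about 18%, 12%, 6% and 1% at ρ = 0.3, 0.5, 0.7 and 0.9. It can cost about 1.5% where the correlation is extremely high or the post SD is well above the baseline SD. It also removes the over-correction of chance imbalance, which is not rare at this size.

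The consequence is moderate. The estimate is an exploratory signal in a feasibility study. It would be wrong to conclude that the 19 per arm or the thresholds for screening (75%), consent (50%) and completion (80%) are undermined, because none of them uses it. What improves is the one quantity the protocol intends to carry into the decision on, and the sizing of, a larger trial. The only TASIT caution is that a within-arm pre-post change should not be read as improvement.

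**What to change.** In section 11.2.2, items 5 and 6, state that for each patient measure the FACES minus control difference will be estimated, with its 95% confidence interval, from a linear model of the post-intervention score on arm and the baseline score of the same instrument. For TASIT this means retest form B on the baseline form, which section 9.4 should name. If CQOLC is compared between arms, use the same model among carers who provide both scores.

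Keep the pre-post changes of section 7.6.2, item 7, as descriptive summaries, with a note that within-arm TASIT change mixes real change with any difference between forms. Report the SDs and the pre-post correlation for each measure, so that the next trial can be sized for the adjusted analysis.

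The cost is a sentence or two of text and one degree of freedom. No new data, visits or patients are needed.

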11.2.3 Parallel Qualitative study

These quantitative measures will be supported by the qualitative results of the lived experience from patients and carers at interview and focus group discussions

11.3 Procedure to account for missing or spurious data

Missing data will be reported and the impact of missing data will be discussed and sensitivity analyses reported according to published standards²⁶. The missing data mechanism will be explored and multiple imputation may be applied as a sensitivity analysis compared to a complete case analysis as appropriate. Other sensitivity analyses will be performed in order to evaluate the robustness of the primary analyses.

11.4 Definition of the end of the study

STAGE 1 will end either; when we understand the intervention and assessments are acceptable to patients and the technique is no longer evolving or; 10 patients have been recruited and undergone their final assessment – whichever is soonest.

Although we expect to screen more patients (up to a maximum of 20), we expect to recruit up to 10 patients to go forwards to the intervention at this stage.

The Study Management Group will look at the data from the patients completing stage 1 to make a decision whether to stop after stage 1 or to continue to stage 2 (See section 11.2.1)

STAGE 2 will end when 19 evaluable patients per arm (intervention and control arms) have undergone their final assessment.

12 Data handling and record keeping

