7.3 Number of Patients

We plan to include a total of approximately 60 patients in this study. Up to 10 patients will take part in interviews prior to Stage 1, approximately 10 in Stage 1 and 38 in Stage 2 (randomised 1:1; 19 receiving the active FACES intervention and 19 receiving the control intervention.)

We will also be inviting patient's carers to take part in interviews/focus groups and to complete a caregiver Quality of Life form forms in Stage 1 and Stage 2.

Separate information sheets and consent forms will be provided for carers.

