7.6 Study Outcome Measures

7.6.1 Stage 1: the cohort study

The specific outcome measures for this part of the study are:

- 1. Percentage of patients completing the intervention (defined as completing all 9 sessions).
- 2. Prospective recording of any changes to the administration, conduct and content of the rehabilitation intervention on a patient-by-patient basis.
- 3. The acceptability of the intervention will be explored through a parallel qualitative study (see below 7.6.3).
- 4. Percentage of patients completing the following validated outcome assessments
 - a. Diagnostic Assessment of Non-verbal Accuracy-2, Adult Faces (DANVA2-AF);
 - b. Emotion Recognition and Social Inference: The Awareness of Social Inference Test (TASIT), (part 1, EET subtest);
 - c. The Toronto Alexithymia Scale-20 (TAS-20).
- Percentage of patients and carers able to complete quality of life questionnaires.

7.6.2 Stage 2: placebo-controlled feasibility randomised controlled trial The outcome measures for this stage will be:

- 1. We will record the number of patients who undergo screening (the numerator) and the number of potentially eligible patients that attend clinic (the denominator). To proceed with a larger, efficacy study we would need to be able to use OCS-Bridge to screen a minimum of 75% of new patients.
- The percentage of screened patients meeting the eligibility criteria provide informed consent for the study. It will also be explored in more detail with the qualitative study (see below).
- 3. Percentage of patients who have completed all sessions for the FACES intervention (active intervention) and General Cognition Intervention (control intervention). To proceed to further studies this will again need to exceed 80%.
- 4. We will measure completion rates for the following established, validated outcome assessments pre- and post-intervention.
 - a. Diagnostic Assessment of Non-verbal Accuracy-2, Adult Faces (DANVA2-AF);
 - b. Part 1, which includes emotion recognition, of Emotion Recognition and Social Inference: The Awareness of Social Inference Test (TASIT);
 - c. The Toronto Alexithymia Scale-20 (TAS-20).

Acceptability will be explored with our parallel qualitative study.

- 5. Patient reported quality of life using the EORTC QLQ-30 with the BN20 brain tumour module¹⁹.
- 6. The impact of these problems on patient's families by asking interested family members to complete the Caregiver Quality of Life Index-Cancer (CQOLC).

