8.4 Subject withdrawal criteria

Patients may withdraw from the trial assessments or from the trial completely, at any time at their own request, or they may be withdrawn at any time at the discretion of the Investigator or Sponsor for safety, behavioural, or administrative reasons.

If the patient withdraws consent for disclosure of future information, no further evaluations should be performed and no additional data should be collected. The Study Management Group (SMG) may retain and continue to use any data collected before such withdrawal of consent.

Patients should be withdrawn from the study and replaced only if the patient requests to be withdrawn.

Procedures and assessments

Summary of the timings and assessments is listed below in the table - Section 9.9.

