9.7 Study Assessments - Post-Intervention

These assessments will be performed before the start of radiotherapy and after completing the three weeks of the intervention. Time points later than this will be confounded by effects of radiotherapy. These assessments will include:

- Diagnostic Assessment of Non-verbal Accuracy-2, Adult Faces (DANVA2-AF);
- 2. Part 1 (EET subtest) of Emotion Recognition and Social Inference (TASIT);
- 3. The Toronto Alexithymia Scale-20 (TAS-20).
- 4. Patient reported quality of life. (EORTC QCQ30 with the BN20)
- 5. Patient's families quality of life.(Caregiver Quality of Life Index-Cancer (CQOLC). http://www.midss.org/content/caregiver-quality-life-index-cancer-cgolc-scale

Quality of life questionnaires will be completed before the clinic visit. If patients or their carers become distressed by the topics raised in the quality of life questionnaires, they will be supported by members of the clinical research team during their clinic visit.

Stage 1 will be used to define which of the assessments that patients are able to complete. These assessments will be used for stage 2.

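### Replacement and end-of-stage rules, with 'evaluable' and the denominator undefined, allow Stage 2 completion rates to be calculated on a set selected for completion

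*Protocol*

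**What the plan says.** - **Size (7.3, also the synopsis).** The plan is "38 in Stage 2 (randomised 1:1; 19 receiving the active FACES intervention and 19 receiving the control intervention". No allowance for drop-out is given.
- **End of Stage 2 (11.4, also the synopsis).** "STAGE 2 will end when 19 evaluable patients per arm (intervention and control arms) have undergone their final assessment". The word 'evaluable' is used only in this rule and is not defined.
- **Replacement (8.4).** "Patients should be withdrawn from the study and replaced only if the patient requests to be withdrawn". The same section says that the Study Management Group "may retain and continue to use any data collected before such withdrawal of consent".
- **Final assessment (9.7).** "These assessments will be performed before the start of radiotherapy and after completing the three weeks of the intervention".
- **Outcome.** For Stage 1, section 7.6.1 gives "Percentage of patients completing the intervention (defined as completing all 9 sessions". For Stage 2, section 11.2.2 says "the percentage of patients who have completed all sessions will be calculated", and sets the rule "Compliance will be concluded if at least 80% of patients complete all sessions". It also measures how many patients complete each outcome assessment before and after the intervention. The denominator of these percentages is described only as patients.

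**The concern.** In a feasibility trial, a patient who finds nine one-hour sessions too much after surgery and asks to leave is the event that the completion rate should record. Section 8.4 replaces that patient, and 11.4 counts progress in patients who reached an assessment placed after the training period. Both rules select on the outcome that the 80% rule measures. If the rate is then taken over the evaluable patients, drop-outs leave the denominator and the rate is too high.

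Completion of the post-intervention assessments is more exposed still. Among patients who are counted because they underwent the final assessment, attendance at that assessment is complete by definition.

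The decision whether to proceed to a larger trial is at stake. The protocol leaves open which denominator applies, so the choice could be made after the data are seen.

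**Working it through.** **1. The plan's own figure.** Section 11.1.2 gives 19 per arm for 80% power, 5% significance and a 50-point difference. The two arm rates are not given. I assume 75% and 25%, two-sided.

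- Uncorrected n = [1.96·√(2·0.5·0.5) + 0.842·√(0.75·0.25 + 0.25·0.75)]² / 0.5² = (1.386 + 0.515)² / 0.25 = 14.5, so 15.
- With continuity correction, n = (14.5/4)·[1 + √(1 + 4/(14.5·0.5))]² = 18.2, so 19.

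The figure reproduces, and 19 is the number before any loss.

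**2. The sections side by side.**

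- 7.3: 2 × 19 = 38 randomised. 11.4: 2 × 19 = 38 evaluable. Both hold only with no attrition, although the 80% rule itself tolerates up to 20% not completing.
- 8.4 replaces a patient only on that patient's request. 11.4 cannot be met until 19 per arm are evaluable, so in effect it replaces anyone who is not evaluable for any reason.

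**3. How few replacements change the decision.** The lowest count that meets 80% of 19 is 16, since 16/19 = 84.2% and 15/19 = 78.9%. Let r be the number of replaced patients in an arm, kept in the denominator as non-completers.

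| Completers among 19 evaluable | Rate on evaluable | Rate on all randomised |
|---|---|---|
| 16 | 84.2% | r = 1: 16/20 = 80.0%; r = 2: 16/21 = 76.2% (fails) |
| 19 | 100% | r = 3: 19/22 = 86.4%; r = 5: 19/24 = 79.2% (fails) |

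The 50% completion rule in 11.1.2 can change in the same way: 10/19 = 52.6%, but with r = 2 it is 10/21 = 47.6%.

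**4. Expected size of the bias.** Let π be true completion among all randomised, and q the share of non-completers who are replaced and left out. Both are assumptions; the protocol gives neither.

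- Apparent rate = π / [π + (1 − π)(1 − q)].
- For π = 0.70 and q = 0.5: 0.70 / (0.70 + 0.30·0.5) = 0.70/0.85 = 82.4%.
- For π = 0.60 and q = 0.5: 0.60 / (0.60 + 0.40·0.5) = 0.60/0.80 = 75.0%.

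The chance of passing is the binomial probability of at least 16 of 19 at the apparent rate.

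| π | q | Apparent rate | P(≥16/19) in one arm |
|---|---|---|---|
| 0.70 | 0 | 70% | 0.13 |
| 0.70 | 0.25 | 76% | 0.29 |
| 0.70 | 0.5 | 82% | 0.56 |
| 0.70 | 0.75 | 90% | 0.90 |
| 0.60 | 0 | 60% | 0.02 |
| 0.60 | 0.25 | 67% | 0.08 |
| 0.60 | 0.5 | 75% | 0.26 |
| 0.60 | 0.75 | 86% | 0.72 |

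**5. Effect on the number randomised.** Reaching 19 evaluable needs 19 / [π + (1 − π)(1 − q)] per arm. For π = 0.70 and q = 0.5 this is 19/0.85 = 22.4 per arm, or about 45 in all, against the 38 in 7.3.

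**The case against.** The strongest reply is that no section makes the evaluable patients the denominator. The term appears in a rule that says when the stage stops, not who is analysed. Section 8.4 allows data collected before withdrawal to be used, and replacing a patient does not delete that patient. With all randomised patients as the denominator, the inflation largely disappears. Analysis sets are also commonly left to the statistical analysis plan.

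This stands against a stronger reading that a reader might infer: that the rate will be computed on completers and reach 100% by construction. The documents do not support that for session completion.

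- Being assessed after the three weeks is not the same as attending all nine sessions. A patient who attends six and is then assessed could be evaluable and still a non-completer.
- The schedule in 9.10 times the visit by the start of radiotherapy, not by session count.
- Section 8.4 replaces only on request, so not every non-completer is replaced under it.

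Two further points on the other side also stand. Nothing says that scores will be analysed other than by randomised arm, and 11.3 already plans missing-data sensitivity analyses, so I make no claim that the score comparison is wrongly specified. Nor does the concern touch the 75% screening rule or the 50% consent rule.

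The reply does not remove the point. Replacement and stopping rules are protocol content, and here they disagree with each other and with the planned number. They also act on the very outcome that the 80% rule measures.

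**Conclusion.** The concern holds as an ambiguity with a known direction. Sections 7.3, 8.4 and 11.4 cannot all be followed once a patient is lost. With 'evaluable' and the denominator undefined, they permit completion rates on a set selected for completion, and any resulting error is upward.

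Two replaced patients in an arm are enough to turn a pass into a fail (16/19 = 84% against 16/21 = 76%). On the assumed rates, replacing half of the non-completers raises the chance of passing in one arm from 0.13 to 0.56 at 70% true completion, and from 0.02 to 0.26 at 60%. If no non-completer is replaced and left out, the bias is zero.

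Two larger figures are tempting but not supported.

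- Pooling the arms (at least 31 of 38) makes the contrast look sharper, but 11.2.2 speaks of the two arms and does not state pooling.
- Dividing 38 by 0.80 to get about 48 randomised, and adding 10 and 10 to reach about 68 patients, treats every non-completer as not evaluable. It also treats the interview patients as separate people, although the synopsis says that they may also take part in Stage 1.

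**What to change.** 1. In 7.6 and 11.2.2, define session completion and assessment completion as the number completing divided by all patients randomised in each arm (Stage 1: all registered). Keep patients who withdraw or are replaced in the denominator as non-completers.
2. Reconcile 7.3, 8.4 and 11.4. Either end Stage 2 on the 38 randomised, once each has had or missed the final assessment, or keep replacement to preserve score pairs. In the second case, define 'evaluable', use it only for the score comparisons, and restate the expected number randomised.
3. Reword 9.7 so that every randomised patient who still consents is invited to the assessment before radiotherapy, whatever number of sessions was completed.

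The cost is a wording amendment before Stage 2, and no more patients if 38 randomised is fixed. The downside is a less favourable completion rate and, with 38 fixed, somewhat fewer complete score pairs.
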